## SCHEMA

Phase I: 12 patients who undergo SBRT and surgical resection

## **PURPOSE**

The purpose of this study is to determine if giving stereotactic body radiation therapy (SBRT) to pancreatic adenocarcinoma before it is surgically resected is safe and feasible.

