### **2.2 Primary Objectives**

- a) To evaluate the feasibility and tolerability of short course preoperative stereotactic body radiation therapy for resectable pancreas cancer
- b) To determine the rate of Grade 2 or greater acute toxicity of neoadjuvant stereotactic body radiation therapy
- c) To determine intraoperative and postoperative surgical morbidity following neoadjuvant treatment including the amount of fibrosis and total operative time.

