## **3. CHARACTERISTIC OF THE RESEARCH POPULATION**

### **3.1 Subject Characteristics**

We aim to enroll 18 patients into this Phase I trial with the goal of 12 evaluable cases. We will recruit from the population of patients who are referred to URMC for diagnosis and workup of their suspected pancreatic adenocarcinoma. We expect that patients will be approximately 50-70 years old with an equal distribution of males and females and racial and ethnic backgrounds. No vulnerable subjects will be enrolled.

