#### 4.3.3 Surgery

Surgery will be performed no more than 3 weeks after completion of radiation therapy. A pancreaticoduodenectomy (Whipple procedure) with standard lymphadenectomy will be done. Restaging is not required prior to surgery. However if re-staging scans are obtained and demonstrate metastatic disease, surgery will not be performed.

An attempted resection may also be aborted when more advanced or metastatic disease is found at the time of laparotomy. If surgical resection cannot be completed due to the presence of advanced disease, the patient will be withdrawn from the protocol at that time and will continue their care with standard treatment and follow up based on their clinical characteristic.

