## **9. DATA ANALYSIS AND MONITORING**

The purpose of this pilot study is to determine feasibility of preoperative SBRT followed by surgical resection at URMC and to determine its safety and tolerability in a small population of patients. For this phase 1 trial, we plan to enroll 18 patients over 1-2 years with a goal of 12 evaluable cases. This is a generally accepted number of patients for phase 1 trials and will minimize the risks to patients in case the treatment is found to be unsafe. We will stop recruitment and analyze the safety data if there appears to be any grade 3 or greater toxicity on any subject that can be directly attributed to SBRT or if any patients are made ineligible for surgical resection solely due to toxicities from SBRT.

In the case where any patient becomes ineligible for resection due solely to toxicity from SBRT, the study will be immediately closed to accrual. We will stop recruitment and any patient who has not started radiation therapy will have their planned radiation treatment canceled. A patient who has started radiation therapy will undergo an individual discussion with [name] about the risks and benefits of continued treatment.

If a patient experiences grade 3 or greater toxicity directly attributable to SBRT that is reversible and ultimately able to undergo resection, we will analyze the event and attempt to prevent/reduce the adverse event from taking place again. We will discuss the risks and benefits of continued recruitment into the study with our co-investigators and determine whether or not to continue the study. If we believe that modifications can be made that will reasonably reduce the risk of a future event from occurring, we will continue recruitment to the study.

The investigators plan to evaluate the rates of acute toxicity after 12 patients have been enrolled and undergone SBRT and surgical resection. Long term safety and efficacy will be evaluated after all 12 patients have undergone surgical resection and have either been followed for at least 6 month or have died. The primary investigator, [name] will have access to all of the study data.

The Cancer Center Data & Safety Monitoring Committee will monitor the study for safety. Study

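### The primary objectives have no feasibility endpoint, denominator or interval estimate, and the 12 evaluable cases appear to be only the patients who reached resection

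*Combined protocol and SAP*

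**What the plan says.** The Purpose section asks a yes/no question: to "determine if giving stereotactic body radiation therapy (SBRT) to pancreatic adenocarcinoma before it is surgically resected is safe and feasible". Section 2.2 lists three primary objectives. Objective (a) reads: "To evaluate the feasibility and tolerability of short course preoperative stereotactic body radiation therapy for resectable pancreas cancer". Objective (b) concerns how often acute toxicity reaches at least grade 2, and objective (c) concerns complications during and after the operation, with fibrosis and operating time named. None carries a definition of success, a denominator or a benchmark.

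On size, Section 3.1 states: "We aim to enroll 18 patients into this Phase I trial with the goal of 12 evaluable cases". Section 9 repeats these numbers and justifies them by convention: "This is a generally accepted number of patients for phase 1 trials". It gives no target rate, precision or drop-out assumption.

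The word evaluable is not defined. The Schema describes the 12 as patients who have SBRT and resection, and Section 9 times the acute toxicity analysis to 12 patients having completed both. Section 4.3.3 withdraws a patient whose resection cannot be completed because of advanced disease.

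Section 9 plans a descriptive report of toxicity and surgical morbidity, with Kaplan-Meier estimates for the oncologic outcomes. It does not mention confidence intervals. It does contain two accrual rules. One patient made ineligible for resection solely by SBRT toxicity closes accrual. One grade 3 or higher event directly attributable to SBRT stops recruitment for a safety analysis, after which the investigators decide whether to go on.

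**The concern.** Feasibility here means that patients get through SBRT and reach surgery on time. That can be measured only in patients who might fail to do so. If the analysis set consists of those who did reach surgery, the main way of failing has been removed before the rate is calculated.

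The same selection affects objective (b). Section 6.1 defines acute toxicity as arising before resection, so a patient who is treated and never resected can have acute toxicity. A rate based on the 12 would leave that patient out.

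Without intervals, a bare 0% or 8% from 12 patients would also look more reassuring than it is, and the plan's size statement does not tell the reader how little the sample can exclude.

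**Working it through.** **1. Can the sample size be reproduced?** No. The documents give no error rate, power, target rate or precision for 12. The 18 implies an allowance of 1 − 12/18 = 33%, which is stated nowhere. The proton study cited in the Background resected 11 of 15, so 4/15 = 26.7% were not resected. Then 12/(1 − 4/15) = 16.4, rounded up to 17. So 18 is plausible as an enrolment allowance, but it is not derived.

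**2. What the denominator does.** Suppose 18 patients start SBRT and 12 are resected, which is the plan's own ratio if all enrolled patients start treatment.

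- Resection among the 12: 12/12 = 100%, whatever the treatment does.
- Resection among all who started: 12/18 = 66.7%.
- Grade 2+ acute toxicity, taking 2 events among the 12 as an illustration: 2/12 = 16.7%. The 6 unresected patients could contribute 0 to 6 further events, so the rate among all treated could lie anywhere from 2/18 = 11.1% to (2 + 6)/18 = 44.4%. The documents do not say where in that range it would fall.

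**3. Precision.** Exact (Clopper-Pearson) two-sided 95% limits for x of n are the 2.5% point of Beta(x, n − x + 1) and the 97.5% point of Beta(x + 1, n − x). For x = 0 the upper limit is 1 − 0.025^(1/n).

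| Result | Estimate | Exact 95% interval |
|---|---|---|
| 0/12 | 0% | 0 to 26.5% |
| 1/12 | 8.3% | 0.2 to 38.5% |
| 2/12 | 16.7% | 2.1 to 48.4% |
| 0/18 | 0% | 0 to 18.5% |
| 12/18 | 66.7% | 41.0 to 86.7% |

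As a yardstick, the Background cites acute grade 3 toxicity in 4 of 15 (26.7%) in the proton study, which also gave capecitabine. A clean 0/12 only just excludes that rate, and 1/12 does not.

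**4. What the Section 9 rules cover.** The chance of at least one event in n patients is 1 − (1 − p)^n. For n = 12 it is 72% at p = 10%, 93% at p = 20% (both assumed rates) and 98% at p = 4/15. The rules are therefore sensitive to severe toxicity. They are silent on the other primary outcomes: grade 2 toxicity in all 12 patients, markedly increased fibrosis, long operations, missed 3-week windows and non-resection for disease would breach neither rule.

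**The case against.** A reader might infer that any result in 12 patients could be called safe and feasible. The documents do not support that. Severe toxicity has consequences fixed in advance: Section 9 closes accrual after one patient loses resection solely to SBRT toxicity and halts recruitment after one attributable grade 3+ event, and Section 6.5 stops SBRT for the affected patient. Nor would 7 of 18 resected pass unnoticed, because it misses the enrolment goal. This part of the objection stands. Its limit is that the rules control accrual and do not define safe or feasible, and that continuation after a reversible grade 3+ event has no numerical bound.

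It is also fair to say that a single-arm pilot needs no hypothesis test, and that a descriptive analysis does not rule out intervals. Both are accepted. The gap is that intervals are not planned and the analysis set is not fixed.

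A second tempting step is to treat 12 of 18 as the success criterion, since it would be met with probability 82% at the cited 11/15 resection rate. That does not hold up:

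- The 11/15 is a resection rate, while a composite of full SBRT and timely resection is stricter. If, by assumption, 90% of resected patients met the other conditions, the per-patient rate would be 0.9 × 11/15 = 66% and the probability would fall to 58%.
- The 18 counts enrolled patients, not those who start SBRT.
- A result of exactly 12/18 has a lower limit of 41.0%.
- The plan presents the ratio as an enrolment goal, not as a test of success.

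**Conclusion.** The point holds in this form: the primary objectives have no feasibility endpoint, denominator or planned interval, and the toxicity rules in Section 9 do not fill that gap. On the natural reading of the Schema and Section 9, the evaluable set is selected on the outcome, so its resection rate is 100% by construction, and acute toxicity in up to 6 of 18 patients could go uncounted.

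This rests on two assumptions: that evaluable means treated and resected, which the plan implies but never defines, and that rates would be computed in that set. If the sponsor already intends to count everyone treated, the remedy is simply to say so. Precision is limited either way, with upper bounds of 26.5% for 0/12 and 38.5% for 1/12. Whether to adopt a pass/fail threshold is a matter of judgement, and its absence is not in itself an error.

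**What to change.** In Sections 2.2 and 9:

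1. Define feasibility per patient as all 5 planned fractions delivered and resection within the window the plan already sets ("Surgery will be performed no more than 3 weeks after completion of radiation therapy").
2. Count every patient who starts SBRT. Tabulate reasons for non-resection separately, toxicity versus disease progression, so that occult disease is not read as a treatment effect.
3. Use the same denominator for grade 2+ acute toxicity, and all resected patients for surgical morbidity, fibrosis and operative time. State that data already collected on patients withdrawn under Section 4.3.3 stay in the analysis.
4. Report each primary rate with an exact 95% interval.
5. Replace the appeal to convention with the precision that 12 to 18 patients give, using the figures above.
6. If a yes/no conclusion is wanted, state the sponsor's own benchmark before the data are seen.

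No extra patients are needed, and neither treatment nor the stopping rules change. Because the primary objectives are reworded, this is a protocol amendment and not only an analysis-plan edit. No form in the protocol lists fractions delivered, so one field should be added. The price is wide intervals and a feasibility rate that will look less favourable than one based on resected patients.

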### **1. BACKGROUND**

Adenocarcinoma of the pancreas is the fourth most common cause of cancer deaths in the United States. Most adenocarcinomas arise in the head of the pancreas in close approximation to the duodenum, celiac axis and superior mesenteric artery. Pancreaticoduodenectomy (Whipple resection) provides the only curative treatment, but only 10-15% of patients are eligible for upfront surgical resection. Unfortunately, even with resection, both locoregional and distant recurrence remains a common problem and 5 year survival rates is 25-30% for patients with node negative disease. Both adjuvant and neoadjuvant therapy have been studied in an attempt to improve current results.

The optimal adjuvant treatment after surgical resection is not currently known. The CONKO-001 trial showed that adjuvant gemcitabine chemotherapy increased 5 year overall survival to 21% from 10% in those who did not receive adjuvant therapy. Whether the addition of radiation therapy to adjuvant chemotherapy is beneficial is controversial. The EORTC 40013/ FFCD-9203/GERCOR phase II study of 90 patients showed that gemcitabine based chemoradiotherapy resulted in improved local control compared with gemcitabine chemotherapy alone with similar median time of disease free and overall survival. The ESPAC-1 trial was a complex study in which patients were randomized to one of 4 adjuvant arms, chemoradiotherapy, chemotherapy, both or none. In a subset analysis of 289 patients, intention to treat analysis showed significantly improved overall survival in patients randomized to receive chemotherapy. On the other hand, patients randomized to chemoradiotherapy had a trend towards worse overall survival. This trial was heavily criticized due to methodological flaws and for using outdated split course radiation techniques. A currently ongoing study RTOG 0848 is seeking to further answer this question by randomizing patients who have received adjuvant chemotherapy to further chemotherapy alone or chemoradiotherapy.

Although upfront surgery with adjuvant therapy is generally chosen, there are many reasons to consider the use of neoadjuvant therapy. The morbidity of surgical resection often prevents the timely delivery of adjuvant therapy. Despite careful technique, there still remains a significant fraction of patients who have positive surgical margins and these patients have a poorer prognosis than those who are able to undergo an R0 resection. Lastly, post-operative

radiation therapy results in the radiation of significant volumes of bowel which often fall into the space previously occupied by the pancreatic head. This can result in significant GI toxicity. As a result, investigators have evaluated the use of neoadjuvant chemoradiation therapy for resectable patients. A study of 50.4 Gy of radiation given over 5.5 weeks in combination with 5-FU demonstrated improved local control versus historical controls. However, toxicity from preoperative treatment resulted in hospital admission for one third of patients. This prompted a consideration of short course preoperative chemoradiation therapy in which 30 Gy in 2 weeks was delivered with concurrent 5-FU which resulted in similar efficacy but decreased grade 3 toxicity. As with most other studies, distant metastases to the liver accounted for a majority of disease progression. Therefore, efforts were made to shorten the interval of neoadjuvant radiation therapy to allow patients to proceed more quickly to surgery and adjuvant chemotherapy which would presumably decrease the rate of metastatic disease.

Short course radiation of 25 Gy in 5 fractions has been extensively studied in Europe for the neoadjuvant treatment of resectable rectal cancer and has been found to improve local control compared to surgery alone. In the Swedish Rectal Cancer Trial, patients underwent resection within 1 week after radiotherapy. A comparison of 25 Gy in 5 fractions to conventional chemoradiation therapy to 50.4 Gy with 5-FU and Leucovorin showed similar rates of survival, local control and late toxicity. In addition, 25 Gy in 5 fractions was associated with less grade 3 or 4 toxicities (3.2% vs. 18.2%, p=<0.001) and higher compliance (97.9% vs. 59.2%) compared with conventional CRT.

Building upon this experience, a prospective study of 15 patients from Harvard demonstrated that neoadjuvant short course RT using 25 Gy in 5 fractions to the pancreatic bed and regional lymph nodes using proton therapy and concurrent capecitabine was feasible and well tolerated. Acute grade 3 toxicity was noted in 4 of 15 patients. 11 of 15 patients underwent surgical resection but no patients experienced delays or exclusion from surgery due to toxicity from neoadjuvant treatment. Evaluation of 30 day post-operative results showed no deaths or anastomotic leaks. 9 of 11 patients who underwent surgery had R0 resections and 10 of these patients were able to receive post-operative gemcitabine. After a median follow up of 12 months, one year overall survival was 75% for the entire group. Of 11 surgical resected patients, 10 are still alive at last follow up. Of 15 patients treated with neoadjuvant therapy, only 1 patient with a positive surgical margin experienced local progression. No patient experienced nodal or regional failure but 8 patients developed metastatic disease.

A similar study was repeated, also at Harvard, using photon (conventional x-rays) instead of proton radiation therapy. However, compared with the proton study a higher rate of fibrosis (63% vs. 27%) was noted during surgery leading to a mean increase in operative time of 69

minutes. Dosimetric comparisons revealed that patients undergoing photon irradiation had significantly increased low dose radiation exposure to the abdominal organs. Due to this complication, the study was terminated after accrual of 10 of 12 planned patients.

While the Harvard study with neoadjuvant proton therapy achieved excellent results, protons are not widely available at most centers including ours. Therefore, we believe that there is a need for continued investigation of neoadjuvant photon radiation therapy for pancreatic cancer. We hypothesize that delivering high dose photon radiation to the gross disease using stereotactic localization (SBRT) without elective nodal irradiation can effectively reduce local recurrence while minimizing the fibrosis noted in the Harvard Photon study.

We are not aware of any prospective reports of using SBRT alone as neoadjuvant treatment for resectable pancreatic cancer. However, there are several single institution experiences which show that SBRT can be safely delivered for locally advanced pancreatic cancer (LAPC). Choung et al. reported treating LAPC with induction chemotherapy followed by 5 fraction SBRT. Dose painting technique of 7-10 Gy/ Fraction to the region of vessel abutment and 5-6 Gy/fraction to the remainder of the tumor was utilized. Of 73 patients evaluated, no patients developed grade 3 or higher acute toxicity and only 5% developed grade 3 or higher late toxicity.

Since SBRT requires large doses of radiation to be accurately delivered, Chuong et al and many other authors have utilized fiducial placement in the tumor for more precise radiotherapy targeting. Although biliary stents have sometimes been used as a surrogate for tumor location, a study of 11 patients demonstrated that biliary stents are not reliable enough to substitute for fiducials in SBRT targeting. Fiducial placement using endoscopic ultrasound (EUS) has been demonstrated to be both feasible and safe.

Based on data from the aforementioned studies, we believe that our protocol which uses photon irradiation of 25 Gy in 5 fractions to the gross disease alone using fiducial localization and stereotactic guidance without chemotherapy will be able to achieve a favorable therapeutic ratio. The rationale is to deliver a dose of radiation that will sterilize microscopic disease at the margins thus decreasing the risk of local recurrence. By targeting the gross disease alone, we hope to minimize the volume of tissue treated and avoid the increase in fibrosis noted in the Harvard photon study. Using radiation therapy alone without chemotherapy will decrease the duration and toxicity of neoadjuvant therapy thereby allowing patients to proceed quickly to definitive surgical resection. After, resection, full dose chemotherapy can then be delivered without interruption with the aim of reducing distant metastatic disease.

## **2. STUDY DESIGN**

### **2.1 Overview**

This will be a Phase I, single center, prospective, single arm feasibility study of the use of stereotactic body radiotherapy (SBRT) for the preoperative treatment of surgically resectable pancreatic adenocarcinoma.

### **2.2 Primary Objectives**

- a) To evaluate the feasibility and tolerability of short course preoperative stereotactic body radiation therapy for resectable pancreas cancer
- b) To determine the rate of Grade 2 or greater acute toxicity of neoadjuvant stereotactic body radiation therapy
- c) To determine intraoperative and postoperative surgical morbidity following neoadjuvant treatment including the amount of fibrosis and total operative time.

### **2.3 Secondary Objectives**

- a) To determine local control and recurrence patterns of treated patients relative to historical controls.
- b) To determine progression free survival of treated patients
- c) To determine overall survival of treated patients

## **3. CHARACTERISTIC OF THE RESEARCH POPULATION**

### **3.1 Subject Characteristics**

We aim to enroll 18 patients into this Phase I trial with the goal of 12 evaluable cases. We will recruit from the population of patients who are referred to URMC for diagnosis and workup of their suspected pancreatic adenocarcinoma. We expect that patients will be approximately 50-70 years old with an equal distribution of males and females and racial and ethnic backgrounds. No vulnerable subjects will be enrolled.

### **3.2 Inclusion Criteria**

- a) Patient with pathologically proven diagnosis of adenocarcinoma of the head of the pancreas
- b) CT w/ contrast or MRI of the abdomen with contrast within 6 weeks prior to registration
- c) CT chest or PET/CT within 6 weeks prior to registration
- d) Clinically determined to be resectable based on NCCN Criteria:

- e) No radiographic evidence of superior mesenteric vein or portal vein distortion
- f) No evidence of distant metastasis
- g) Clear fat planes around the celiac axis, hepatic artery, and superior mesenteric artery
- h) No enlarged lymph nodes per CT criteria or PET avid lymph nodes
- i) No lymphadenopathy outside the surgical field (i.e. celiac or para-aortic adenopathy)
- j) Adequate cardiopulmonary reserves to tolerate surgery
- k) Karnofsky performance status  $\geq 70$
- l) Age  $\geq 18$
- m) Adequate bone marrow function defined as follows:
  - Absolute neutrophil count (ANC)  $\geq 1800$  cells/mm^3
  - Platelets  $\geq 100,000$  cells/mm^3
  - Hemoglobin  $\geq 8.0$  g/dl (Note: The use of transfusion or other intervention to achieve Hgb  $\geq 8$  g/dl is acceptable.)
- n) Pregnancy test must be negative for women of childbearing potential within 7 days prior to study entry
- o) Patient must sign study specific informed consent prior to study entry

